Demographic and baseline clinical and disease characteristics will be summarized in tables. For continuous variables the summary will include number, mean, and standard deviation and 95% confidence intervals. Summaries for categorical variables will include the number and percent of subjects in each category.

Imputation for Missing Data

Imputations for missing data in (e.g. withdrawn subjects, loss to follow-up, missing data) will not be performed. Analyses will be performed with all available data only.

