In order to approximate the performance rates for this study, the results from the El Camino Hospital (ECH) Study were used. The PQB procedural approach was evaluated in the ECH Study. This study used a similar technique to the interventional approach utilized in the ECH Study. This study also used a stent graft that is very similar to the stent graft used in the ECH Study, the Gore Viabahn Stent Graft. Primary patency at 6 months was approximately 90% in the ECH Study. A more conservative estimate of 85% performance for the PQ Bypass Systems was utilized along with the aforementioned performance goal for the purpose of sample size estimation. To achieve 80% power using a one-sided alpha of 0.05, the sample size is 50. To adjust for lost to follow-up and to maintain consistency with current literature on the use of stent grafts, 60 subjects will be enrolled in this study ((Table 11-1)).

Table 11-1: Non-Inferiority with PQ Bypass Performance of 85%

PG	NI Margin				
	5%	7.5%	10%	12.5%	15%
80%	103	69	50	38	30
85%	368	174	103	69	50
90%	-	1371	368	174	103
95%	-	-	-	1371	368

The sample size was also elected in order to observe the rate of major adverse events. The median number of patients enrolled in stent graft trials reported in the literature is 59 patients (range 15-144).

Surgical Bypass Studies

Clinical data published on existing surgical bypass studies for treating femoropopliteal disease is more limited quantitatively and qualitatively. Most importantly, few studies involve doppler-ultrasound assessments of arterial velocity as a basis of assessing patency (e.g. peak systolic velocity ratio). However, one particular and recent randomized prospective study of the Gore Viabahn stent graft vs. prosthetic bypass surgery provides very reliable data set on surgical outcomes as illustrated in **Table 11-2**.

The randomized prospective study was designed to compare the effectiveness of treating superficial femoral artery occlusive disease percutaneously with expanded polytetrafluoroethylene (ePTFE)/nitinol self-expanding stent grafts vs surgical femoral-to-above knee (AK) popliteal artery bypass with synthetic graft material.

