Stent graft	35	1 (13)	7 (10)	0.735	(0.587, 0.837)

CI, Confidence interval.

Log-rank $P = .895$.

*Number in parenthesis represents cumulative events or censored observations through end of interval.

Table V. Secondary patency in femoropopliteal bypass group and stent graft group

Time post-treatment (months)	N at risk at start of interval	N events during interval*	N censored during interval*	% Free from loss of patency	95% CI
Operative (day 0-30)					
Fem-pop bypass	50	2 (2)	0 (0)	0.960	(0.849, 0.990)
Stent graft	50	0 (0)	0 (0)	1.000	(1.000, 1.000)
3 months (day 31-136)					
Fem-pop bypass	48	2 (4)	1 (1)	0.920	(0.801, 0.969)
Stent graft	50	6 (6)	1 (1)	0.880	(0.752, 0.944)
6 months (day 137-227)					
Fem-pop bypass	45	3 (7)	2 (3)	0.859	(0.726, 0.930)
Stent graft	43	1 (7)	1 (2)	0.860	(0.728, 0.930)
9 months (day 228-319)					
Fem-pop bypass	40	1 (8)	8 (11)	0.837	(0.701, 0.915)
Stent graft	41	1 (8)	1 (3)	0.839	(0.703, 0.916)
12 months (day 320-456)					
Fem-pop bypass	31	0 (8)	11 (22)	0.837	(0.701, 0.915)
Stent graft	39	0 (8)	9 (12)	0.839	(0.703, 0.916)

CI, Confidence interval.

Log-rank P value = .861.

*Number in parenthesis represents cumulative events or censored observations through end of interval.

Kedora et al J Vasc Surg 2007;45:10-16

McQuade et al J Vasc Surg. 2009 Jan;49(1):109-15

In order to establish a sample size, a margin of non-inferiority, delta, was set at 10% for the current study to demonstrate non-inferiority of the PQ Bypass Systems to the historical control in terms of patency. This delta reflects the limited quantitative and qualitative availability of fem-pop bypass studies in the literature. Therefore, a 10% delta is adequate to accurately reflect non-inferiority. This delta sets up a comparison between the lower 95% CI of the PQ Bypass Systems performance to the lower 95% CI reported for the competitive products (~70%).

As such using as historical control rate of 80-85% and a non-inferiority margin of 10%, the null and alternative hypotheses of the primary performance endpoint can be written as:

$$H_0: \pi_{PQB_performance} \leq \pi_{PG_performance}$$

$$H_A: \pi_{PQB_performance} > \pi_{PG_performance}$$

where,

$$\pi_{PG_performance} = 85\% \text{ historical control rate} - 10\% \text{ Delta}$$

$$\pi_{PQB_performance} = \text{PQB Systems success rate}$$

The hypotheses for the primary performance endpoint can be rewritten as:

$$H_0: \pi_{PQB_performance} \leq 70\%$$

$$H_A: \pi_{PQB_performance} > 70\%$$

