A conservative estimate of 85% performance for the PQ Bypass Systems was utilized along with the aforementioned performance goal for the purpose of sample size estimation. To achieve 80% power using a one-sided alpha of 0.05, the maximum sample size required is 103 subjects. As the surgical patency rate is extrapolated to be between 82% and 85% and since no loss to follow-up is expected in the study, a sample size of 100 subjects should be sufficient and enrolled in this study (**Table 11-3**).

Table 11-3: Non-Inferiority with PQ Bypass Performance of 85%

PG	NI Margin				
	5%	7.5%	10%	12.5%	15%
80%	103	69	50	38	30
85%	368	174	103	69	50
90%	-	1371	368	174	103
95%	-	-	-	1371	368

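### The 100-subject size rests on an unsupported no-loss assumption; at the 75% surgical goal the stated 80% power is modestly missed

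*Combined protocol and SAP*

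**What the plan says.** Section 11.2, under Surgical Bypass Studies, sizes the study against a surgical control of 85% less a 10-point margin. For the device, "A conservative estimate of 85% performance for the PQ Bypass Systems was utilized". The result is "To achieve 80% power using a one-sided alpha of 0.05, the maximum sample size required is 103 subjects".

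The plan then adopts 100 on two grounds. The surgical 6-month patency is extrapolated to lie between 82% and 85%, and "since no loss to follow-up is expected in the study, a sample size of 100 subjects should be sufficient". The protocol summary and Section 5.4 make 100 a ceiling.

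Other places bear on the second ground:

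- Section 11.2, Stent Graft Studies, computes 50 and then says "To adjust for lost to follow-up and to maintain consistency with current literature on the use of stent grafts, 60 subjects will be enrolled".
- Section 11.1, on missing data, names withdrawn and lost subjects, rules out imputation and adds "Analyses will be performed with all available data only". It also bases the primary endpoints on a per-protocol analysis.
- Table 11-2 shows 3 of 50 bypass limbs and 2 of 50 stent-graft limbs censored by the end of the 6-month interval.

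The goal itself is not stated consistently. The surgical part of Section 11.2 defines it as 85% minus 10%, but then writes the null as 70% or less. Section 11.1 also compares the lower confidence bound with 70%.

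**The concern.** The figure of 103 counts subjects with an outcome, because the formula behind it contains no allowance for loss. Enrolling at most 100 and analysing only available data therefore yields 80% power at the 75% goal only if the planned number is slightly generous and nobody is lost. Neither condition holds by the plan's own formula.

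The zero-loss premise also conflicts with how the same section handled the same endpoint in the first phase. A reader who takes the 80% at face value could misjudge what a missed 75% goal means.

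**Working it through.** **Inputs.** One-sided alpha 0.05, power 80%, device patency p1 = 0.85 and a 10-point margin, all from Section 11.2. The goals p0 are 0.75 (85% control), 0.72 (82% control, the low end of the plan's range) and 0.70 (the printed null and Section 11.1). Losses of 4% and 6% are 2/50 and 3/50 from Table 11-2. A loss of 10% is an assumption, since the plan gives no rate for the 100.

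**Reproducing the plan.** The one-sample normal approximation is

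n = [1.645·√(p0(1−p0)) + 0.8416·√(p1(1−p1))]² / (p1−p0)²

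- p0 = 0.75: (0.7122 + 0.3005)² / 0.10² = 102.57, so 103, as printed.
- p0 = 0.70: (0.7538 + 0.3005)² / 0.15² = 49.40, so 50, as printed.
- p0 = 0.72: (0.7385 + 0.3005)² / 0.13² = 63.88, so 64.

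Every filled cell of Tables 11-1 and 11-3 reproduces in this way. The 103 is therefore correct, and it belongs to the 75% goal.

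**Power for a given evaluable n.** The same formula, solved for power, is

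Φ{[(p1−p0)·√n − 1.645·√(p0(1−p0))] / √(p1(1−p1))}

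At p0 = 0.75 and n = 100 this is Φ[(1.0000 − 0.7122)/0.3571] = Φ(0.806) = 79.0%. At n = 90 it is Φ[(0.9487 − 0.7122)/0.3571] = Φ(0.662) = 74.6%.

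The exact column uses the Score lower bound named in Section 11.1. It finds the smallest number of patent grafts whose bound exceeds 75%, then takes the binomial probability of reaching that number when true patency is 85%.

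| Evaluable n | 75% goal, formula | 75% goal, exact Score (patent grafts needed; true alpha) | 72% goal, formula | 70% goal, formula |
|---|---|---|---|---|
| 103 | 80.2% | 80.3% (85; 4.6%) | 94.8% | 98.4% |
| 100 | 79.0% | 76.3% (83; 3.8%) | 94.2% | 98.2% |
| 96 (4% loss) | 77.3% | 81.4% (79; 5.9%) | 93.3% | 97.8% |
| 94 (6% loss) | 76.4% | 76.1% (78; 4.4%) | 92.8% | 97.5% |
| 90 (10% loss) | 74.6% | 73.0% (75; 4.0%) | 91.7% | 97.0% |

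The exact figures saw-tooth because the required count is a whole number. The 81.4% at 96 comes with a true alpha of 5.9%, above the nominal 5%. The formula column is the fairer summary of the trend.

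**The case against.** The strongest reply is that the comparison Section 11.1 will actually make is against 70%. There, 100 subjects give 98% power and even 90 give 97%. This stands: no shortfall exists at that goal, and a reader who infers that the trial as a whole is underpowered goes further than the documents allow.

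Second, the plan gives two grounds for 100, and the first has weight. It calls 103 a maximum, at the top of an 82-85% range, and the surgical 6-month rate in Table 11-2 is 81.8%. At an 82% control only 64 are needed. At 84%, 87 are needed and 90 evaluable give 81.6%. At 84.5%, 94 evaluable still give 80.0%, though 90 give 78.3%. This also stands, and it confines the shortfall to the top of the range.

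Third, the gap between 100 and 103 costs only about one point of power, and exact Score power is above 80% at 96. Both are correct. A requirement of 103 for 80% therefore holds under the normal approximation and is not a general threshold. Exact power is nonetheless below 80% at 100, 94 and 90.

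Fourth, a reader might treat the step from 50 to 60 as a 16.7% loss allowance (10/60) and apply it to the 100, giving about 71% power. The documents do not support that reading, because the step was also made for consistency with the literature. It shows only that some loss was expected.

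Fifth, Section 6.5 sets a procedure for lost subjects and forecasts no rate, so attrition is likely rather than certain. Finally, Section 11.1 disclaims formal hypothesis testing and any required sample size. That lowers the stakes, but Section 11.2 still states hypotheses, alpha and power and uses them to justify 100.

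**Conclusion.** The point holds in a limited form. The no-loss premise has no support in the documents and conflicts with the first-phase sizing, the missing-data rule and the censoring in the plan's own comparator trial. Because the plan needs only 50 subjects against 70%, the increase to 100 rests on the 75% surgical goal. At that goal the stated 80% is not reached by the plan's own formula: 79.0% with complete data, about 77% at 4% loss, 76% at 6% and 75% at 10%.

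These figures assume true patency of 85% and a surgical control of exactly 85%; the 10% loss is assumed. At the 72% and 70% goals power stays above 90% throughout this range. The arithmetic behind 103 is correct. The fault is an unsupported assumption, together with a goal stated as 75% for sizing and 70% for testing. Meeting 70% would not show non-inferiority to an 85% surgical rate within a 10-point margin.

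**What to change.** In Section 11.2:

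- Delete the statement that no loss is expected.
- State the power that 100 enrolled subjects deliver over a stated loss range, for example 0-10%, at each goal: 79% falling to 75% at 75%, 94% falling to 92% at 72%, and 98% falling to 97% at 70%.
- Say that 103 evaluable subjects for 80% power applies to the 75% goal under the normal approximation, and that exact Score power does not change smoothly with n.
- Do not present the step from 50 to 60 as a 16.7% loss allowance.
- Reconcile the 75% goal used for sizing with the 70% in the surgical hypothesis and in Section 11.1.

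No extra subjects, visits or procedures are needed. The only cost is a slightly less favourable stated power at the 75% goal.

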12.0 ADVERSE EVENTS

The occurrence of Adverse Events will be monitored during this study. All Adverse Events will be recorded on the Complication/Adverse Event Form at onset and at each follow-up visit until resolved.

Potential adverse events associated with use of the Stent Graft System (SGS) SGS include, but are not limited to the following:

 Access site hemorrhage or hematoma Access site pain/infection Acute vessel closure Aneurysm or pseudoaneurysm formation Arteriovenous (AV) fistula 	
 Inflammation Malposition Myocardial infarction Radiation injury Renal insufficiency/failure due to excessive
--	--

 • Death • Device failure • Embolism • Fever/pain in absence of infection • Infection 	
 • contrast load • Sepsis • Shock • Side branch occlusion • Stenosis or Occlusion • Thrombosis • Vessel dissection, perforation or wall trauma
--	---

Potential adverse events associated with use of the Guidewire Delivery System (GWDS) include, but are not limited to the following:

 • Access site hemorrhage or hematoma • Access site pain • Acute vessel closure • Bleeding complications • Vessel dissection, perforation or wall trauma 	
 • Death • Embolism • Infection • Renal insufficiency/failure due to excessive contrast load
---	--

Potential adverse events associated with use of the Balloon Dilator (BD) include, but are not limited to the following:

 • Hemorrhage or hematoma • Hypotension • Pain • Arrhythmias • Systemic embolization • Endocarditis • Pyrogenic reaction • Acute vessel closure • Vascular Thrombosis • Bleeding complications • Sepsis/Infection 	
 • Short term hemodynamic deterioration • Drug reactions, allergic reaction to contrast media • Aneurysm or pseudoaneurysm formation • Death • Renal insufficiency/failure due to excessive contrast load • Vessel dissection, perforation or wall trauma • Potential balloon separation following rupture or abuse and subsequent need to use a snare or other medical interventional techniques to retrieve the pieces
--	---

To meet the objectives of this study, the following definitions will apply. (Definitions reference ISO 14155:2011-01)

12.1 Adverse Event (AE)

Adverse Event (AE): Any untoward medical occurrence, unintended disease or injury or any untoward clinical signs (including an abnormal laboratory finding) in subjects, users or other persons whether or not related to the medical device. This includes events related to the device or events related to the procedures involved.

Adverse Device Effect: An adverse event related to the use of a medical device, including adverse events resulting from insufficient or inadequate Instructions for Use, deployment, implantation, installation or operation, or any malfunction of the medical device or any event resulting from user error or intentional misuse of the medical device.

The Investigator is responsible for assessing the severity of the AE, the causal relationship between any events and the clinical study procedure, activities or device. Additionally, the Investigator is responsible for providing appropriate treatment for the event and for adequately following the event until resolution. The following categories of adverse event severity are to be used:

- Mild: Awareness of a sign or symptom that does not interfere with the subject's usual activity or is transient, resolved without treatment and with no clinical sequelae.
- Moderate: Interferes with the subject's usual activity.
- Serious: Any fatal or immediately life-threatening clinical experience that requires a subject to be hospitalized, or hospitalization is unduly prolonged because of potential disability or danger to life or because an intervention has been necessitated. This includes any permanently disabling event.

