11.0 ENDPOINTS AND STATISTICAL ANALYSIS PLAN

11.1 Endpoints Analyses and Reporting of Results

The study objective is to assess the safety and performance of the PQ Bypass System to access, deliver guidewires and implant stent grafts for a percutaneous fem-pop bypass.

The study is a feasibility study with no formal hypothesis testing and therefore no required sample size. Study results will be presented using descriptive statistics. Results from this study will be used to design additional clinical studies.

All subjects will be followed on an intent-to-treat basis. The device performance will be assessed based on a per-protocol analysis of the primary safety and effectiveness endpoints. An Intent-to-treat analysis, along with other secondary analyses, will also be completed and reported.

Demographic, baseline clinical and disease characteristics, procedural results and primary, secondary and all additional endpoints will be summarized using descriptive statistics.

All statistical analyses will be performed using SAS for Windows version 9.1 or higher.

Primary Safety Endpoint Reporting:

Safety assessment is achieved by recording and measuring Major Complication rates/Serious Adverse Event rates associated with the PQ Bypass procedure. The number and percentage 6-month MAE will be presented using descriptive Statistics. Using the Score approximation, the one-sided upper 95% confidence bound will be calculated and presented.

Primary Performance Endpoint Reporting:

Descriptive statistics of the primary performance endpoint which includes total number of patent PQB grafts, number and percentage of patent PQB grafts, and the one-sided 95% CI of the percentage using the Score approximation will be presented. The lower bound of the one-sided 95% CI will be compared to the performance goal of 70% (80% historical control rate – 10% Delta.)

Secondary Endpoint Analysis:

The secondary endpoint of primary assisted and secondary patency will be summarized using Kaplan-Meier survival analysis. Life tables will be created and a Kaplan-Meier survival curve will be presented.

The secondary endpoints of Procedural Success, Clinical Success and Technical

Success will be summarized by providing point estimates, number of subjects, and 95% confidence bounds calculated using the Score approximation.

Demographic, procedural and safety data:

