12.2 Serious Adverse Event (SAE)

Serious Adverse Event (SAE): A serious adverse event is any problem or unwanted event encountered in a clinical trial or a performance evaluation that has led, or could have led, directly or indirectly to death or to a serious deterioration in the health of a subject or user or any other person, without regard to whether the event was caused by a medical product. (§ 2 no. 5 MPSV). The following events (including laboratory results and outcome events) will be considered to be SAEs and must immediately (within 24 hours) be reported to the study Sponsor by telephone, fax and/or email. These events must be reported whether or not the Investigator believes they are related to study procedures, activities or device:

- Death
- Serious deterioration in the health of the subject, that either resulted in
 - a life-threatening illness or injury, or
 - a permanent impairment of a body structure or a body function, or
 - in-patient or prolonged hospitalization, or
 - medical or surgical intervention to prevent life-threatening illness or injury or permanent impairment to a body structure or a body function.
 - Malignant Tumor (Austrian Medical Device Act, § 3 Abs.16 MPG as amended)

Serious Adverse Device Effect: An adverse device effect that has resulted in any of the consequences of a Serious Adverse Event.

Note: Planned hospitalization for a pre-existing condition, a condition unrelated to the treatment or a procedure required by this study, that is without serious deterioration in health, is not considered a serious adverse event.

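### Section 12.1 uses 'Serious' as its top AE severity grade, with criteria that differ from the SAE definition in 12.2, and has no 'Severe' grade

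*Combined protocol and SAP*

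**What the plan says.** Section 12.1 introduces its scale with "The following categories of adverse event severity are to be used" and lists three grades.

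- The lowest begins "Mild: Awareness of a sign or symptom that does not interfere with the" subject's usual activity. It also takes in transient events that resolve untreated and leave no sequelae.
- The middle grade is "Moderate: Interferes with the subject's usual activity", with no upper limit.
- The top grade is labelled 'Serious'. It opens "Serious: Any fatal or immediately life-threatening clinical experience that requires a subject to be hospitalized", continues "or hospitalization is unduly prolonged because of potential disability or danger to life or because an intervention has been necessitated", and closes "This includes any permanently disabling event".

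Section 12.2 then defines a Serious Adverse Event for itself. It covers problems that led, or could have led, to death or serious deterioration in health. Its list includes death without condition, "in-patient or prolonged hospitalization, or" preventive medical or surgical intervention, and malignant tumor. A note excludes certain planned hospitalizations. Section 19 restates the SAE definition in wider words, adding events that might lead to such harm.

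Severity is used elsewhere. Section 12.4 makes it an item of the event report. Section 12.3 makes it one of the features by which a device effect is judged unanticipated against the risk analysis report. Section 11.1 rests the safety assessment on "recording and measuring Major Complication rates/Serious Adverse Event rates associated with the PQ Bypass procedure".

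No section says that the 12.1 'Serious' grade is distinct from SAE status, or which definition governs if they disagree.

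**The concern.** Severity (how intense an event is) and seriousness (whether it meets a regulatory outcome criterion) are separate attributes. Section 12.1 merges them: its two lower grades are based on interference with usual activity, and its top grade on outcome. The label on that top grade is also the word that 12.2 defines by other criteria.

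Two things follow. The scale has nowhere to put an event that is severe in intensity but does not meet the outcome criteria. And one event can be an SAE under 12.2 while its severity field says it is not 'Serious', with no text telling the site or the analyst that the two uses differ. At stake are the content of a required report field, the unanticipated-effect judgment that draws on severity, and a clear source for the SAE counts in 11.1.

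**Working it through.** No arithmetic applies. The check sets the criteria of 12.1 and 12.2 side by side.

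The first 12.1 clause can be read in two ways. Read strictly, hospitalization is a further condition on a fatal or immediately life-threatening event. Read loosely, any hospitalization is enough. Both readings are shown.

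| Event | 12.2 SAE | 12.1 'Serious', strict | 12.1 'Serious', loose |
|---|---|---|---|
| Fatal or life-threatening, hospitalized | Yes | Yes | Yes |
| Permanent disability | Yes | Yes | Yes |
| Unplanned admission from serious deterioration, not immediately life-threatening | Yes | No | Yes |
| Intervention to prevent permanent impairment, no admission or prolonged stay | Yes | No | No |
| Event that only could have led to death or serious deterioration, no admission | Yes | No | No |
| Malignant tumor, not life-threatening or disabling, no admission | Yes | No | No |

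The last three rows differ on either reading. In the intervention row, the 12.1 phrase about a necessitated intervention qualifies the prolongation of a hospital stay. If it were detached and read as a criterion of its own, that row would also close, but the last two would not. Events in these rows default to Moderate if they interfere with usual activity, and otherwise possibly to Mild.

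Next, the missing grade. Take an event that stops the subject's usual activity altogether for a time but needs no admission and leaves no permanent disability. It is not Mild, unless it is transient and resolves untreated, and it does not meet 'Serious'. Only Moderate is left, the same grade as slight interference.

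Finally, where each definition is used:

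- **24-hour reporting.** Section 12.2 attaches the rule to its own list and 12.6 repeats it for all SAEs. Section 12.4 extends it to UADEs and to events possibly related to the device or procedure. None of these refers to the 12.1 grade.
- **Primary safety endpoint.** MAE is death, target vessel revascularization or target limb amputation. It does not use the severity scale.
- **Severity field.** It is required by 12.4 and is an input to the UADE and USADE definitions in 12.3. This is where 12.1 takes effect.

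**The case against.** The strongest reply is that an SAE of moderate severity is ordinary, so different answers from 12.1 and 12.2 are no error in themselves. That is right as a principle, and a corrected scale would still allow a moderate SAE. It does not rescue 12.1, which uses the word 'Serious' with its own outcome criteria as a grade of intensity.

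It can also be said that the top-grade sentence is garbled: read strictly, a death outside hospital would miss its first clause, which cannot be intended. That stands, and it is why the point does not rest on the hospitalization row.

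Four stronger readings are tempting, and the documents do not support them.

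- A reader might infer that 24-hour reporting turns on the 12.1 word. It rests on 12.2, 12.4 and 12.6. A UADE is by definition device-related, so 12.4 already covers it.
- A reader might infer two competing SAE rates. Section 11.1 uses the defined term, and no text says to count SAEs from the severity grade. The documents also give no readmission rate from which a difference could be sized.
- A reader might infer that investigators will under-call SAEs. That is a prediction. Section 12.2 gives them an explicit list, and Section 13.0 requires 100% verification of adverse events.
- A reader might infer that planned severity tables are spoiled. Section 11 specifies none.

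The AE form is not among the documents, so a separate seriousness item may already exist.

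**Conclusion.** Wrong as written. The 12.1 scale has no 'Severe' grade, and its 'Serious' grade conflicts in wording with the SAE definitions in 12.2 and Section 19. Under the stated rule, some SAEs fall outside 'Serious', and some incapacitating events can only be Moderate.

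The consequence is limited. The severity field may be wrong or ambiguous, the unanticipated-effect judgment loses a distinction it needs, and the field may be mistaken for SAE status. Reporting timelines, the MAE endpoint and the sample size are unaffected. The number of events involved cannot be derived from the documents.

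The conclusion assumes that the form follows the 12.1 wording for severity. It does not depend on which reading of the hospitalization clause is taken.

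**What to change.** 1. In 12.1, replace the 'Serious' grade with a 'Severe' grade based on intensity, continuing the interference-with-activity scale of the two lower grades (for example, usual activity prevented). Delete the fatal, life-threatening and hospitalization wording from the scale.
2. State that seriousness is a separate attribute defined only by 12.2, and align the SAE entry in Section 19 with it.
3. State in 11.1 that SAE rates are counted from that attribute and not from the severity grade.
4. Confirm that the AE form has a separate seriousness item, and add one if it does not.
5. For events already recorded (Section 2.4 reports 60 subjects treated by May 2016), check that SAE status follows 12.2 and re-map the 'Serious' grade where needed, within the existing 100% monitoring of adverse events. A full regrade of every Moderate event is not called for. The report can note that Moderate grades given before the change may include some events that would now be Severe.

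The cost is protocol wording, possibly one form field, and a limited review of recorded events.
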